- b) Positive history of chronic gastrointestinal diseases, or systemic disease that could affect gastrointestinal motility, or use of medications that may alter gastrointestinal motility, appetite or absorption, e.g., orlistat, within the last 6 months.
- c) Significant untreated psychiatric dysfunction based upon screening with the Hospital Anxiety and Depression Inventory (HAD), and the Questionnaire on Eating and Weight Patterns (binge eating disorders and bulimia). If such a dysfunction is identified by an anxiety or depression score > 11 or difficulties with substance or eating disorders, the participant will be excluded and given a referral letter to his/her primary care doctor for further appraisal and follow-up.
- d) Hypersensitivity to any of the study medications.
- e) No contraindications to the FDA-approved medications: Phentermine-Topiramate Extended Release; Phentermine; Oral naltrexone extended-release/bupropion extended-release (NBSR; Contrave[®], Mysimba[™]); and Liraglutide (Saxenda[®]).
- f) Participants who meet the following criteria:
 - a. No match to any phenotype based upon 90th and 75th percentile criteria; or
 - b. Matches 2 or more phenotype based upon 90th percentile criteria; or
 - c. No match to phenotype based on 90th percentile criteria and 2 or more match to phenotype based upon 75th percentile criteria
- g) Sub Study specific exclusion criteria
 - a. Any contraindications to MRI
 - b. Claustrophobia

Anthropometrics and phenotype studies

Anthropometrics Measurements: will be taken of hip-waist ratio, height, weight, blood pressure, pulse at baseline, randomization day and week 12.

Phenotype studies at baseline:

Participants will attend the Mayo Clinic Clinical Research and Trials Unit after an 8-hour fasting period, and the following validated quantitative traits (phenotypes) will be measured at baseline:

- o) The DEXA scan (dual energy x-ray absorptiometry) will measure body composition.
- p) Resting energy expenditure: was assessed by indirect calorimetry with a ventilated hood (Parvo Medics, Sandy, UT).

- q) Gastric emptying (GE) of solids by scintigraphy: The primary endpoint is gastric half-emptying time (GE $t_{1/2}$) [3, 51, 52].
- r) Appetite (hunger level) by visual analog score fasting and after standard meal for GE and prior to the Satiation test [3].

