f. Exercise behavior - The Exercise Regulations Questionnaire (BREQ-3)[65] and its subsequent modifications have become the most widely used measures of the continuum of behavioural regulation in exercise psychology research. It has been used either as a multidimensional instrument giving separate scores for each subscale, or as a unidimensional index of the *degree of self-determination*.

g. Barriers to Increasing Physical Activity Participation - Barriers to Being Active Quiz, *What keeps you from being more active?*[66].

h. Three Factor eating questionnaire is 51-item questionnaire, validated, to assess for emotional eating disorders and food cravings.

i. Bowel Disease Questionnaire

Standard of Care:

All participants will receive standard of care which consists of 1) Intense lifestyle intervention, behavioral evaluation and treatment, and a medication as part of the regular clinic management for obesity.

Intense Lifestyle Intervention and Behavioral Treatment

All the participants will meet the multidisciplinary team which consists of an Obesity Expert physician and a CRTU registered dietitian nutritionist as standard of care in our clinical practice. These appointments will be scheduled in the CRTU. All participants will be guided to 1) Nutrition: Reduce dietary intake below that required for energy balance by consuming 1200calories per day for women and 1400calories per day for men; 2) Physical Activity: reach the goal of 10,000 steps or more per day; 3) Exercise: reach the goal of 150 minutes or more of cardiovascular exercise/week; 4) Limit consumption of liquid calories (i.e. sodas, juices, alcohol, etc.). All participants will receive a personal fitness tracker, where their activity and calories will be tracked. This information will be given in a booklet format.

[figure not shown]
Pharmacotherapy for obesity

Pharmacotherapy for the treatment of obesity can be considered if a patient has a body mass index (BMI) $\geq 30 \text{ kg/m}^2$ or BMI $> 27 \text{ kg/m}^2$ with a comorbidity such as hypertension, type 2 diabetes, dyslipidemia and obstructive sleep apnea[16]. Medical therapy should be initiated with dose escalation based on efficacy and tolerability to the recommended dose. We do an assessment of efficacy and safety at 4 weeks. In both groups, medications will be assessed for drug interactions and potential side effects as standard of care.

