Medication selection: Once the phenotype tests are completed the results will be filled in an algorithm to assist on the decision of the medication selection based on our previous data [3, 5, 11, 13]. The algorithm for phenotype selection will be based on the following decision tree (as figure below) 1) Participant will complete the ALL phenotype testing; 2) abnormal phenotype will be selected if participant meets criteria for one variable greater or lower than 90% of median (values described in table below); 3) if match to two or more abnormal (90% percentile) values, participant will be excluded; 4) if no abnormal ($<$ or $>$ 90%) value, the abnormal phenotype will be selected based on the value with $<$ or $>$ 75%; 5) if there are two or more abnormal values (75% percentile), patient will be excluded; 6) if participants do not have any abnormal value (based upon 90% of 75%) will be excluded.

TEST	Abnormal result					Example	Example	Example	Example
	Females		Males			1	2	3	4
	(90%)	(75%)	(90%)	(75%)	Female	Male	Male	Female	
Satiation (Ad libitum)	> 1065 kcal	> 894 kcal	> 1962 kcal	> 1376 kcal	1400 kcal	1000 kcal	1100 kcal	850 kcal	

Buffet Meal)								
Satiety (Gastric emptying SGE $T^{1/2}$)	< 97 min	< 101 min	< 76 min	< 86 min	102 min	80 min	105 min	110 min
Behavioral Traits (Questionnaires)	HADS > 9 points	HADS > 7 points	HADS > 10 points	HADS A > 7 points	5	4	9	3
Energy Expenditure (Resting EE)	< 93% predicted	< 96% predicted	< 88% predicted	< 94% predicted	102%	98%	95%	92%
Phenotype				-	Ab Satiety	Ab Satiety	Ab Psych	Ab E.E.

Once the decision is made on the “phenotype-guided” medication, pharmacy will assess whether patient is randomized to “intervention” or “control”. Based on the randomization, patient will pick up the prescription for 3 months.

Phentermine prescribed subjects will be recommended to involve into resistance training routines. During the 3 month visit, participants will be offered a prescription to continue the medication (if randomized to the intervention group) or switch to the phenotype guided medication (if randomized to the control group). Patients who continue obesity pharmacotherapy will be contacted every three months for one year to monitor their weight and comorbidities.

Control group: Pharmacotherapy for obesity

Standard of care pharmacotherapy for obesity recommends the following doses and regimen for weight loss:

- Phentermine: 15 mg oral daily

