- Phentermine-Topiramate Extended Release (Qsymia®) at dose of 7.5/46 mg oral daily
- Oral naltrexone extended-release/bupropion extended-release (NBSR; Contrave®) at dose of 32/360 mg oral daily (divided in 2 tablets in morning and 2 tablets in evening)
- Liraglutide (Saxenda®) at dose of 3 mg subcutaneous daily

There is currently no gold-standard or first choice for obesity pharmacotherapy and physicians select the medication to use on their patients based on comorbidities, previous experience, safety or adverse events. Thus, in this protocol, the FDA-approved medications will be randomly selected. The physician will review the “selection” to assess for potential contraindications, adverse events and/or drug-drug interactions per inclusion and exclusion criteria.

Intervention group: by obesity phenotype guided pharmacotherapy

Participants in the intervention group will have 4 tests to assess 1) satiation, 2) Satiety/return to hunger, 3) behavioral, or 4) energy expenditure. As described on Figure 8 pharmacotherapy will be guided based on the “abnormal” phenotype (following algorithm described above). In case of a mixed pattern or multiple abnormal phenotypes, patient will be excluded from study and referred to weight management clinic.

Algorithm diagnostic:

1. satiation: Phentermine-Topiramate Extended Release (Qsymia®) at dose of 7.5/46 mg oral daily
2. Satiety/return to hunger: Liraglutide 3 mg SQ daily
3. Behavioral/Psychological: Oral naltrexone extended-release/bupropion extended-release (NBSR; Contrave®) at dose of 32/360 mg oral daily (divided in 2 tablets in morning and 2 tablets in evening); or
4. Energy expenditure: Phentermine 15 mg daily plus increase physical activity and resistance training.

General Principles of Statistical Analyses

Primary endpoint: Total Body Weight Loss, kg (defined as weight changed from baseline to 12 weeks) in the obesity phenotype-guided pharmacotherapy (intervention) vs. the randomly assigned pharmacotherapy (control) group in patients with obesity and an abnormal obesity-related phenotype.

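### Exclusion criterion e is worded the wrong way round, and the physician's contraindication review of the selected drug is written for the control group only

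*Combined protocol and SAP*

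**What the plan says.** Four places in the combined protocol and SAP bear on this.

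- **Exclusion criteria (under Selection Participants).** Item e reads "No contraindications to the FDA-approved medications" and names phentermine-topiramate ER, phentermine, naltrexone/bupropion and liraglutide. In the same list, item d is "Hypersensitivity to any of the study medications" and sub-study item g.a is "Any contraindications to MRI".
- **Pharmacotherapy for obesity.** "In both groups, medications will be assessed for drug interactions and potential side effects as standard of care". The sentence follows one about an efficacy and safety assessment at 4 weeks, and gives no time of its own.
- **Medication selection and Control group.** The phenotype-guided drug is decided first. Then "pharmacy will assess whether patient is randomized to" intervention or control. For controls, "Thus, in this protocol, the FDA-approved medications will be randomly selected", and the next sentence has the physician review the selection "to assess for potential contraindications, adverse events and/or drug-drug interactions per inclusion and exclusion criteria". The Intervention group section has no such sentence.
- **Study Design, and Randomization and Allocation.** Physicians, study team and participants are blinded, and allocation is concealed. The abstract gives medication selection to a pharmacist outside the study.

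**The concern.** Item e is an operative eligibility rule that bears on safety. Staff applying it have to guess its direction, and the text does not say whether a contraindication to any one of the four drugs is decisive or only one to the drug allocated. Scope matters because the inclusion criteria admit people with controlled comorbidities, while the protocol's Background reports guideline advice against phentermine and phentermine-topiramate in cardiovascular disease. By the protocol's own account, suitability can differ between the drugs.

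The placement of the physician review raises a second problem. A check on the drawn drug that is written for one arm can reveal the arm to the person doing it. If a finding led to a different drug, to no drug or to removal, it would also act on one arm only. Controls' drugs would then no longer be a purely random draw, or the control group would lose a selected subset. The statistical section defines no analysis population and sizes the trial on 200 completers, so it says nothing about how such participants would be counted.

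**Working it through.** This is a check of wording and procedure. No figure in the plan depends on it.

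**Background: the plan's sample size is not at issue.** Inputs from the sample size section: difference 7.3 − 6.1 = 1.2 kg, SD 2.8 kg, two-sided alpha 0.05, power 80%.

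- Normal approximation: n = 2 × (1.96 + 0.842)² × 2.8² / 1.2² ≈ 85.5, so 86 per group.
- Two-sample t-test: 86.4, so 87 per group, as stated.
- Inflation: 87 / (1 − 0.13) = 100 per group, and 200 / (1 − 0.20) = 250. Both match the plan.

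Rewording item e changes none of these.

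**Step 1, polarity of item e.** An item in an exclusion list states the condition that removes a person. Items d and g.a do so: hypersensitivity present, or an MRI contraindication present, means excluded. Item e states the absence of the condition. Applied literally, it removes those with no contraindication and keeps those with one. It is therefore inverted, and the neighbouring items show the likely intent.

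**Step 2, which checks exist and for whom.**

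| Check | Contraindications named? | Arms | Timing |
|---|---|---|---|
| Exclusion d | Hypersensitivity only | Both | Eligibility |
| Exclusion e | Yes, but inverted | Both | Eligibility |
| Pharmacotherapy for obesity | No (interactions, side effects) | Both | Not stated |
| Physician review of the selection | Yes | Written for control only | Not stated; placed after the random selection |

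Once item e is set aside as defective, the only remaining sentence that uses the word contraindications for a study drug is the one under the control heading.

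**Step 3, against the blinding text.** A physician who reviews a drug selection only for controls learns the arm from being asked. The blinding statements say physicians do not know it. The two can be reconciled only if the review is done in both arms, or before the arm is known. The protocol says neither.

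**Step 4, consequence of a positive finding.** No passage says whether the drug is redrawn, replaced or withheld, or whether the participant is excluded.

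**Step 5, size.** If a fraction f of controls were dropped after review, and their mean weight loss differed by d kg from that of the remaining controls, the control mean would move by f × d. The documents give neither f nor d. If drugs were replaced instead, the shift would depend on differences between drugs in this population, which are also not given. No bias can be calculated.

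**The case against.** The strongest reply is that this is a drafting slip with little behind it. Item e names all four drugs and sits beside correctly worded items, so any trained site would read it as intended. The control-group review refers back to the eligibility criteria and so presupposes a sensible item e. Assessment of interactions and side effects is promised in both groups, which covers much of what the control-group sentence lists. Much of this stands, and it rules out several stronger readings that a reader might infer.

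- *That the trial screens for drug-specific problems only after allocation.* Exclusion d is a correctly worded screen in both arms, and the evident intent of item e is another.
- *That the drug can be altered in the control arm only.* The text says that the physician reviews and assesses. It authorises no veto, redraw or substitution in either arm, and that the review follows allocation is inferred from where the sentence stands.
- *That the reviewing physician is unblinded.* This follows only if the review is confined to controls and the physician knows it.
- *That a sound item e would leave the review with nothing to do.* The review also covers adverse events and drug-drug interactions, which item e does not list.

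What the reply does not remove is that the rule is wrong on the page, its scope is unstated, and the contraindication review is written for one arm in a trial that promises blinded physicians.

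**Conclusion.** The point holds as one of wording and consistency. The inversion of item e is certain from the text. So is the asymmetry: physician review of the selected drug for contraindications appears under control and has no counterpart under intervention. Two consequences are conditional on the review being run as written, in controls alone: disclosure of the arm to a physician meant to be blinded, and departures from the allocated drug that differ by arm. The second also requires that a positive finding leads to some change, on which the protocol is silent. The documents do not show that either has happened or must happen, and they give no rate from which a bias in the 1.2 kg comparison could be estimated. Sample size, power and alpha are unaffected.

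**What to change.** 1. Reword item e so that its direction matches items d and g.a, and state which of the listed drugs it covers.
2. Reconcile the exclusion criteria, the Pharmacotherapy for obesity section and the Control group section so that one contraindication and interaction check is done identically for every participant and completed before randomisation.
3. Keep any later safety review, but make it identical in both arms and done without knowledge of arm. State who does it, when, and what follows a positive finding.
4. State in the statistical section that anyone whose drug is later withheld or changed is analysed in the arm assigned.

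Which conditions count as contraindications, and how they are managed, is for the sponsor and investigators.

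The cost is a small protocol rewording and moving a review earlier. Depending on the scope chosen for item e, a few more people may be excluded before randomisation, which would narrow the population slightly but would not unbalance the arms.

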- f) Satiety will be measured in length of time of fullness at Ad-libitum meal
- g) Self-administered questionnaires assessing affect, physical activity, attitudes, body image, and eating behavior;
- h) Plasma gastrointestinal hormones (Total and active Ghrelin, GLP-1, CCK, PYY and bile acids) by RIA
- i) Targeted Metabolomics
- j) Blood DNA stored
- k) Stool sample stored
- l) Saliva samples stored
- m) Flexible sigmoidoscopy and biopsies of left colon for mRNA, DNA, protein studies
- n) Pseudo-continuous arterial spin labeling (pCASL) functional brain MRI study paradigm

Medication selection by a non-study pharmacist will be randomized and double blinded (physician, study team and participant) according to the FDA-approved medicine suggested by the phenotype or to another FDA-approved medicine not suggested by the phenotype.

Follow-up: All participants will be seen at 4 and 12 weeks (+/- 4 days) (current standard of practice). All participants will receive standard intense lifestyle interventions, which consists of one visit with CRTU registered dietitian. At 10 weeks (+/- 2 weeks) of treatment, participants will have a repeat flexible sigmoidoscopy and a pCASL functional brain MRI study paradigm. At the 12-week visit, participants will be unblinded to their “obesity-related phenotype” and they could contact their physician to discuss continuation of a FDA-approved medication as clinically indicated and recommended by their physician. Study team will prospectively follow the patients’ weight and waist circumference, as well as any pharmacotherapy followed for obesity every 3 months for 1 year.

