Primary endpoint: Total Body Weight Loss, kg (defined as weight changed from baseline to 12 weeks) in the obesity phenotype-guided pharmacotherapy (intervention) vs. the randomly assigned pharmacotherapy (control) group. The secondary end points will be percentage of responders (defined as number of participants who loss 5% or more of total body weight) compared to baseline in the obesity phenotype guided pharmacotherapy (intervention) group vs. standard of care at 4 and 12 weeks; percentage of responders with at least 10 and 15% at 12 weeks, and 10% at 6 months and 12 months; percentage of responders at 5%, 10% and 15%; percentage of responders within each obesity-phenotype group at 4 and 12 weeks; side effects of medications; changes in blood flow in the brain areas, and transcriptomic changes in colonic mucosa. In the open-label extension, we will assess the total body weight loss at 24 and 52 weeks in both groups.

Sample size assessment: In order to account for dropouts and to detect an effect size in weight loss between groups of interest (intervention vs. control) we propose a randomized, double-blinded, active controlled trial of 250 participants with obesity to compare effects of Intervention compared to Control in weight loss. In our recent pilot study [with Liraglutide 3.0 mg vs. placebo], the SD for the overall weight change (pre-post) observed was 2.8kg. Using this SD, we have estimated the differences between groups that could be detected with approximately 80% power (2-sided α level of 0.05) for main effects. The analysis will involve an ANCOVA models, with the response being actual weight change; the covariates to be considered include gender, and weight at baseline. We noticed a 20% withdrawal rate during the study, thus, we extended the enrolled number to aim to have 200 participants complete the study.

Significance: Our study individualizes obesity treatment to maximize pharmacotherapy outcome based on phenotyping obesity at baseline.

BACKGROUND

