In a 12 week, randomized, double-blinded, active controlled trial, with 9 month open-label extension of 250 participants with obesity; we will compare the weight loss response rate to obesity-phenotype-guided pharmacotherapy (intervention) vs. non-phenotype guided (randomly selected) pharmacotherapy (control) in patients with obesity. All 250 participants will be phenotyped and the medication selection will be randomly and double blinded (to physician, study team and participant) to the FDA-approved medicine suggested by the phenotype or to another FDA-approved medicine not suggested by the phenotype. A computer generated randomization schedule generated by the study statistician's office will be submitted to the Mayo Clinic CCaTS Research Pharmacy. Allocations will be concealed. This study will be blinded until data are transmitted to the statistician for data lock. All participants will receive a standard intense lifestyle intervention, which consists of 1 visit with registered dietitian. The phenotypic studies include (all performed in same day in the following order): Fasting blood collection, resting energy expenditure, gastric emptying

with meal for breakfast, behavioral questionnaires, and buffet meal test for lunch. Blood will be collected assessment of metabolomic biomarkers, gastrointestinal hormones, and DNA (blood and buccal swab). Stool samples for microbiome and bile acid. Saliva samples for assessment of metabolomic biomarkers. Participants will return to the CRTU to pick up medication based on the randomization and a personal fitness tracker. All participants will be seen at 4 and 12 weeks (+/- 4 days) (current standard in practice). Participants will keep a medication diary, which will have to be returned on the 12-week visit. A saliva, stool and fasting blood sample, and DEXA will be done at the 12-week visit. At the 12-week visit, participants will be unblinded to their "obesity-related phenotype" and they could contact their physician to continue a FDA-approved medication as part of clinical care. Study team will prospectively follow the patients' weight, waist circumference and use of obesity medications every 3 months for 1 year. In a sub-study, 40 participants will complete at baseline and at 10 weeks (+/- 2 weeks), a flexible sigmoidoscopy and a pCASL functional MRI; with the intention to study the effects of pharmacotherapy in gut mucosa and brain blood flow changes at baseline and after treatment.

Randomization and Allocation

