The secondary end points will be percentage of responders (defined as number of participants who loss 5% or more of total body weight) compared to baseline in the obesity phenotype guided pharmacotherapy (intervention) group vs. standard of care at 4 and 12 weeks; percentage of responders with at least 10 and 15% at 12 weeks, and 10% at 6 months and 12 months; percentage of responders at 5%, 10% and 15%; percentage of responders within each obesity-phenotype group at 4 and 12 weeks; side effects of medications, pharmacogenomics role to weight loss, side effect and; changes in blood flow in the brain areas, and transcriptomic changes in colonic mucosa.; the performance of the PHENO-Test in predicting the obesity phenotype and the weight loss outcome based on the test when comparing phenotype-guided intervention vs. controls. In the open-label extension, we will assess the total body weight loss at 24 and 52 weeks in both groups.

Statistical Analyses: We propose a randomized, double-blinded, active controlled trial of 200 participants with obesity to compare effects of Intervention compared to controls in weight loss. The analysis will involve an ANCOVA models, with the response being actual weight change; the covariates to be considered include gender, and weight at baseline.

Sample size assessment and power calculation: The detectable effect size in weight loss between groups of interest (intervention vs. control) is given in the table below. In our recent pilot study [with Liraglutide 3.0 mg vs. placebo], the SD for the overall weight change (pre-post) observed was 2.8kg [32]. Using this SD, we have estimated the differences between groups that could be detected with approximately 80% power (2-sided α level of 0.05) for main effects. Thus, the sample size needed is 87 participants per group. In order to account for a maximum dropout rate of 13%, we will randomize 100 participants per group. An interim assessment will be done when 50% of the patients have completed the study for the purposes of assessing data quality and the power calculation assumptions. Specifically, that the weight change standard deviation is 2.8 and the dropout rate is 10-13%. No calculation of the treatment difference will be

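### The month-3 switch offer limits what the 6- and 12-month results can show by arm, and one follow-up sentence could restrict late weights to patients still on drug

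*Combined protocol and SAP*

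**What the plan says.** **What is offered at month 3.** Under Pharmacotherapy for obesity, the Medication selection text offers intervention participants a prescription to carry on with their drug. Controls are offered the chance to "switch to the phenotype guided medication (if randomized to the control group".

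**Who is followed afterwards.** The same paragraph ends: "Patients who continue obesity pharmacotherapy will be contacted every three months for one year to monitor their weight and comorbidities". Two other sections describe follow-up without that condition:

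- Abstract, Follow-up: participants learn their phenotype at week 12 and "they could contact their physician to discuss continuation of a FDA-approved medication as clinically indicated and recommended by their physician". The study team follows the patients' weight and waist circumference, "as well as any pharmacotherapy followed for obesity every 3 months for 1 year".
- Study Design: after unblinding to phenotype, "they could contact their physician to continue a FDA-approved medication as part of clinical care". The team follows weight, "waist circumference and use of obesity medications every 3 months for 1 year".

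**Which late endpoints are listed.** The secondary list, in the Abstract and in General Principles of Statistical Analyses, opens with 5% responders in the guided "group vs. standard of care at 4 and 12 weeks". After a semicolon comes "percentage of responders with at least 10 and 15% at 12 weeks, and 10% at 6 months and 12 months". A final sentence places total body weight loss at 24 and 52 weeks, in both groups, in the open-label extension. The primary endpoint is weight change from baseline to 12 weeks.

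**The concern.** Two things bear on the late endpoints.

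First, whether a patient continues an obesity drug is known only after randomisation. It plausibly depends on weight lost so far, on tolerability and on arm, because the two arms are offered different things at month 3. If late weights are collected only from continuers, randomisation no longer protects the comparison. Late weights not taken on schedule cannot be recovered.

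Second, once controls have been offered the guided drug, neither arm represents unguided treatment. A small late difference could be misread as guidance that does not last. A persisting one could be misread as lasting superiority over standard of care. Neither conclusion would follow.

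**Working it through.** No figure in the plan is in dispute here, so the check is mainly of the texts against each other.

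**1. Follow-up population.**

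| Section | Who is followed | What is recorded |
|---|---|---|
| Abstract, Follow-up | the patients, no condition | weight, waist, obesity drugs |
| Study Design | the patients, no condition | weight, waist, obesity drugs |
| Medication selection | those continuing an obesity drug | weight, comorbidities |

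The third row is narrower in who is contacted, although it adds comorbidities. It does not say that the others are dropped. It also gives no instruction to contact them.

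**2. What restriction to continuers would do.** In arm z (1 = guided, 0 = control), let k_z be the share continuing, and m_C,z and m_S,z the mean late losses of continuers and stoppers. The arm mean is k_z·m_C,z + (1 − k_z)·m_S,z. The continuers' mean therefore exceeds the arm mean by (1 − k_z)(m_C,z − m_S,z). The continuers-only difference departs from the full randomised difference by

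(1 − k_1)(m_C,1 − m_S,1) − (1 − k_0)(m_C,0 − m_S,0).

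This is zero only if the two terms match. The plan states none of the four quantities (two continuation shares and two continuer-minus-stopper gaps), so the sign and the size are both unknown.

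**3. What the arms compare if everyone is followed.** Guided participants are offered guidance from the start. Controls are offered it 12 weeks later, after 12 weeks assigned to control pharmacotherapy.

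| Time point | Guided arm: weeks since offer | Control arm: weeks since offer |
|---|---|---|
| 12 weeks | 12 | 0 |
| 24 weeks | 24 | 24 − 12 = 12 |
| 52 weeks | 52 | 52 − 12 = 40 |

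The 6- and 12-month responder rates fall at about the same times as the last two rows. Uptake is left to participants and physicians, so these are the longest possible times on guided drug, not expected ones. The comparison by randomised arm remains valid, but it estimates the effect of an immediate versus a delayed offer.

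**4. Labelling.** The 24/52-week weight endpoint is explicitly assigned to the open-label extension. The 6/12-month responder rate is not; it sits among the week-4 and week-12 secondary endpoints.

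**5. Primary endpoint and sample size.** With SD 2.8 kg, a difference of 7.3 − 6.1 = 1.2 kg, two-sided α 0.05 and 80% power, the normal approximation is n = 2(1.960 + 0.842)² × 2.8²/1.2² ≈ 85.5, so 86 per group. The two-sample t-test gives 86.4, so 87, which is the plan's figure. Allowing for 13% dropout, 87/0.87 = 100 per group; for 20% withdrawal, 200/0.80 = 250 in total. The primary endpoint ends at week 12, before any switch takes effect, so none of this changes.

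**The case against.** The case on the other side is substantial, and most of it stands as a limit on the point.

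- **A reader might infer that the plan promises guided therapy versus standard of care at one year.** It does not. The standard-of-care comparator is attached to weeks 4 and 12. The 6/12-month rate follows with no comparator, and assessing the 24/52-week endpoint in both groups promises no between-arm test. The hypothesis is also set at 12 weeks. The risk is over-interpretation of late data, not a false claim in the text.
- **A reader might infer that patients who stop are lost by design.** Two sections follow the patients unconditionally, and recording drug use makes sense if some are off drug. The bias arises only if the Medication selection sentence overrides them. That is possible, because it is the most specific instruction on quarterly contact after the month-3 offer.
- **A reader might infer two incompatible week-12 procedures.** They can coexist: a participant may be offered a prescription and also discuss it with a physician. Aligning the wording is optional editing.
- **A reader might try to size the bias in kilograms from the liraglutide stopping rule (loss of 4% or less at 16 weeks).** That rule is background text, not a trial rule. It also falls after controls have already been offered a switch at month 3, and it would need an assumed baseline weight and drug share.
- **A reader might want the late comparison demoted to descriptive.** With complete follow-up it is a valid randomised contrast, so that label is a preference. The absence of a named analysis set is not particular to the extension either, since the plan names none for any endpoint.

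Two things remain after this: the narrower follow-up sentence, and the need to say what the late contrast means once controls have been offered the guided drug.

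**Conclusion.** The point holds as a minor one and is a cheap improvement. The month-3 offer means that the 6/12-month and 24/52-week results, taken by arm, can compare at most an immediate with a 12-week-delayed offer of guidance. The Medication selection sentence, if applied literally, would also select the late weights on an event after randomisation. The size is unknown, and any selection bias could go either way, because the plan gives no continuation, switch or stopping rates.

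This rests on two assumptions: that the switch is offered as written, and, for the selection part, that staff follow the narrower sentence rather than the two broader ones. Only secondary and extension endpoints are touched.

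**What to change.** 1. Amend Medication selection so that weight and obesity-drug use are collected quarterly up to one year for every randomised participant, on or off drug, in line with the Abstract and Study Design.
2. Place the 10% responder rate at 6 and 12 months in the open-label extension, beside the 24/52-week weight endpoint.
3. State that all late endpoints are analysed by original randomised arm and interpreted as immediate versus delayed offer of guidance.
4. Report the shares of controls who switched, kept their drug or stopped.

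The cost is wording, plus contacts that two sections already promise; the drug-use data are already planned. The downside is a weaker long-term claim, though it is the one the design supports. The follow-up wording should be settled before extension contacts begin.
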